8. DEFINITION OF ANALYSIS POPULATIONS

The "Safety" population will consist of all subjects who received at least one dose of LY3154885 or placebo.

The "PK" population will consist of all subjects who received at least one dose of LY3154885 and have evaluable PK data.

All protocol deviations that occur during the study will be considered for their severity/impact and will be taken into consideration when subjects are assigned to analysis populations.

9. STATISTICAL METHODOLOGY

9.1 General

Data listings will be provided for all data that is databased. Summary statistics and statistical analysis will only be presented for data where detailed in this SAP. For continuous data, summary statistics will include the arithmetic mean, arithmetic standard deviation (SD), median, min, max and N; for log-normal data (e.g. the PK parameters) the geometric mean and geometric coefficient of variation (CV%) will also be presented. For categorical data, frequency count and percentages will be presented. Data listings will be provided for all subjects up to the point of withdrawal, with any subjects excluded from the relevant population highlighted. Summary statistics and statistical analyses will generally only be performed for subjects included in the relevant analysis population. For the calculation of summary statistics and statistical analysis, unrounded data will be used.

Mean change from baseline is the mean of all individual subjects' change from baseline values. Each individual change from baseline will be calculated by subtracting the individual subject's baseline value from the value at the timepoint. The individual subject's change from baseline values will be used to calculate the mean change from baseline using a SAS procedure such as Proc Univariate.

Data analysis will be performed using SAS[®] Version 9.4 or greater.

9.2 Demographics and Subject Disposition

Subject disposition will be listed. The demographic variables age, sex, race, ethnicity, body weight, height and body mass index will be summarized by part and listed. All other demographic variables will be listed only.

9.3 Pharmacokinetic Assessment

9.3.1 Pharmacokinetic Analysis

The PK parameter estimates for LY3154885 will be calculated by standard noncompartmental analysis methods. Parameters for analysis will be maximum observed drug concentration (C_{max}), time to C_{max} (t_{max}), and area under the concentration versus time curve (AUC) of LY3154885 following single and multiple doses of LY3154885. Following multiple dosing, accumulation ratios based on LY3154885 AUC will be calculated as follows: AUC Day 14 / AUC Day 1 and AUC Day 7 / AUC Day 1. Other PK parameters such as half-life, apparent clearance, and apparent volume of distribution may be reported using noncompartmental analysis methods.

If appropriate data are obtained, renal clearance of LY3154885 will be calculated as the ratio of amount excreted/AUC. This will be compared to the unbound glomerular filtration rate, which is estimated using creatinine clearance.

If available, plasma concentration data for itraconazole and its metabolites (if applicable) will be summarized or listed in the CSR, and the data may subsequently be used for exploratory model development. A noncompartmental PK analysis of itraconazole and its metabolites may be conducted if deemed valuable to the interpretation of the study results but is not required to complete the CSR.

9.3.2 Pharmacokinetic Statistical Methodology

Statistical analysis of the PK parameters will be produced by Covance. All summary outputs will be produced by Lilly.

Part A: The PK parameters C_{max} and AUC for LY3154885 will be evaluated to estimate the dose-exposure proportionality of LY3154885 using a linear-mixed-effect power model. In this model, log-transformed dose will be the independent variable and subject will be a random effect. Both C_{max} and AUC will be log-transformed prior to analysis. The least-squares (LS) means for each treatment together with the treatment differences and associated 90% confidence intervals (CIs) will be estimated from the model. These estimates will be back-transformed to present geometric means, the ratios of geometric means, and the corresponding 90% CIs.

Example SAS code for the analysis:

```
proc mixed data=xxx;
  class subject;
  model log_pk = log_dose / alpha=0.1 cl solution outpred=resids ddfm=kr;
  random subject;
  estimate 'xx mg' intercept 1 log_dose yy / alpha=0.1 cl; /*Log value of xx*/
  estimate 'zz mg - xx mg' log_dose pp / alpha=0.1 cl; /*Difference in log
  values of zz and xx*/
  ods output solutionf=est estimates=estims;
run;
```

Part B: The PK parameters C_{max} and AUC for LY3154885 when administered alone and with itraconazole will be compared using an analysis of variance (ANOVA) model. The parameters will be log-transformed prior to analysis. The model will include a fixed-effect for the treatment (LY + itraconazole : LY) and a random effect for subject. The LS means for each treatment, the difference between the treatment LS means (LY3154885 + itraconazole – LY3154885), and the associated 90% CIs will be estimated from the ANOVA model and back-transformed from the log scale to provide estimates of the geometric means, geometric mean ratio, and corresponding 90% CIs.

Example SAS code for the analysis:

```
proc mixed data=xxx;
  class treatment subject;
  model log_pk = treatment / residual ddfm=kr;
  random subject;
  lsmeans treatment / cl pdiff alpha=0.1;
  ods output lsmeans=lsm diff=estims;
run;
```

The t_{max} of LY3154885 for both treatments will be analyzed using a Wilcoxon signed-rank test. An estimate of the median difference and 90% CI will be calculated.

Part C: The plasma PK parameters C_{max} and AUC for LY3154885 obtained on Day 14 will be evaluated to estimate the dose-exposure proportionality of LY3154885 using a linear-mixed-effect power model. The model used will be the same as Part A above but without subject as a random effect.

Part D:

Effect of formulation: The AUC and C_{max} for LY3154885 following administration of a capsule and tablet formulation in a fasted state will be log transformed and analyzed using a mixed effects ANOVA model. The model will include fixed effects for formulation (capsule : tablet) and a random effect for subject. The LS means for each formulation and the 90% CI for the difference in means will be estimated from the ANOVA model and back-transformed from the log scale to provide estimates of the geometric means and 90% CIs for the ratio of the means.

The t_{max} of LY3154885 between formulations will be analyzed using a Wilcoxon signed-rank test. An estimate of the median difference and 90% CI will be calculated.

Effect of high-fat diet: The AUC and C_{max} for LY3154885 following administration of a tablet formulation in the fed state and fasted state will be log transformed and analyzed using a mixed-effects ANOVA model. The model will include fixed effects for food (fed : fasted) and a random effect for subject. The LS means for fed and fasted and the 90% CI for the difference in means will be estimated from the ANOVA model and back-transformed from the log scale to provide estimates of the geometric means and 90% CIs for the ratio of the means.

The t_{max} of LY3154885 between fed and fasted will be analyzed using a Wilcoxon signed-rank test. An estimate of the median difference and 90% CI will be calculated.

The SAS code for both analyses will be similar to the Part B analysis.

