5.1 Part A (Single-Ascending Dose)

Part A will be conducted in 2 alternating cohorts (Cohorts 1 and 2), each consisting of approximately 12 subjects who will participate in up to 3 study periods. The planned doses of LY3154885 to be tested are 15, 45, 100, 200, 400, and 500 mg.

Sentinel dosing will be used in Part A of the study. For all dose levels, LY3154885 and placebo will be administered first to 2 subjects (1:1 LY3154885:Placebo) in a blinded manner. These subjects will be followed up for 24 hours postdose; if the dose is well tolerated, dosing of the remaining 10 subjects in the cohort at the same dose level may begin.

Each subject in Cohorts 1 and 2 will be randomized to receive 2 single oral doses of LY3154885 and 1 oral dose of placebo as a capsule formulation over 3 study periods in a crossover fashion. For each study period, it is intended that 8 subjects will receive LY3154885 and 4 subjects will receive placebo.

In Period 1, subjects will be admitted to the clinical research unit (CRU) on the evening of Day -2. A 24 hour baseline ambulatory blood pressure monitoring (ABPM) recording on Day -1 of Period 1. ABPM recording on dosing days will be initiated 2 hours prior to dose for Periods 1, 2 and 3. Subjects will undergo an overnight fast before dosing with LY3154885 or placebo as a single oral dose on Day 1 and will remain inpatient for at least 48 hours after dosing (until Day 3), after which they may be discharged at the discretion of the investigator. The washout time

between doses for a given subject will be at least 7 days. A post study follow-up visit will be conducted at least 7 days after the final dose.

All available safety data, including adverse events (AEs), vital signs (blood pressure [BP] and pulse rate [PR]), electrocardiogram (ECGs), and clinical laboratory tests, from all subjects dosed will be assessed prior to escalating to the next dose level. Safety data must include data from at least 2 days from a minimum of 6 subjects who received LY3154885. The investigator and sponsor will review the data, with the investigator remaining blinded. If dose escalation is terminated prior to reaching Dose 6 because of tolerability issues, previous dose levels may be repeated or lower/intermediate dose levels may be tested.

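### The Part A and Part C per-dose means and dose ratios are predictions from a log-log line but are labelled as treatment estimates, and no check of that line is specified

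*SAP*

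**What the plan says.** SAP 9.3.2 states the aim for Part A: Cmax and AUC "will be evaluated to estimate the dose-exposure proportionality of LY3154885 using a linear-mixed-effect power model". In that model "log-transformed dose will be the independent variable and subject will be a random effect". It then promises more than a slope: "The least-squares (LS) means for each treatment together with the treatment differences and associated 90% confidence intervals (CIs) will be estimated from the model", back-transformed to geometric means and their ratios. Protocol 10.3.2.2 has the same text.

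The example code shows how these are obtained. The CLASS statement names only subject, and the model line is "model log_pk = log_dose / alpha=0.1 cl solution outpred=resids ddfm=kr". A per-dose mean comes from "estimate 'xx mg' intercept 1 log_dose yy / alpha=0.1 cl" and a difference between doses from "estimate 'zz mg - xx mg' log_dose pp / alpha=0.1 cl". For Part C (Day 14), the SAP says: "The model used will be the same as Part A above but without subject as a random effect".

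Two other provisions bear on the point. Protocol 10.3.2.2 plans descriptive PK statistics by treatment, and SAP 9.1 includes the geometric mean and geometric CV% among them. The code also writes residuals to a data set, but the text gives them no use.

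**The concern.** A reader of the report will take a treatment LS mean to be an estimate from the data at that dose, and a treatment difference to be a comparison of the data at two doses. Part B in the same section uses the words in that sense, with treatment in the CLASS and LSMEANS statements. In Part A they mean a point on a fitted line and a multiple of its slope.

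If log exposure is linear in log dose, this is efficient and correct. If it is not, the tabulated ratios cannot show it, because every one of them is computed from the same slope. The intervals would look very precise at the top of the dose range, where a departure from proportionality would matter most for planning later studies.

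**Working it through.** The documents give no variance, power or precision figure, so there is no planned figure to reproduce. The CVs and exposure shapes below are assumptions.

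**Inputs from the documents**
- Doses (SAP 5.1): "The planned doses of LY3154885 to be tested are 15, 45, 100, 200, 400, and 500 mg".
- Two alternating cohorts of 12, each subject with two active doses and one placebo. This gives 24 × 2 = 48 active profiles, or 8 per dose.
- By the Part A design figure, Cohort 1 gets Doses 1, 3 and 5 and Cohort 2 gets Doses 2, 4 and 6. Every adjacent-dose comparison is therefore between cohorts.

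**Step 1: what the code estimates.** With intercept a and slope b:
- mean at dose D: exp(a + b ln D)
- ratio of D2 to D1: exp(b [ln D2 − ln D1]) = (D2/D1)^b
- SE of the log ratio: |ln(D2/D1)| × SE(b)

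All dose ratios share one t statistic. The per-dose means also use the intercept, so their CIs are not just a rescaled slope.

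**Step 2: CI widths.** These use generalised least squares on the planned layout, with random subject and known variances. Log-scale variance is ln(1 + CV²). The t quantile is 1.711 (24 df) for the line and 1.725 (20 df) for dose as a class effect, standing in for Kenward-Roger.

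| | CV 20/30% | CV 25/40% |
|---|---|---|
| SE(b) | 0.027 | 0.033 |
| 500/400, line: exp(1.711 × SE(b) × ln 1.25) | ×/÷ 1.010 | ×/÷ 1.013 |
| 400/200, line: exp(1.711 × SE(b) × ln 2) | ×/÷ 1.03 | ×/÷ 1.04 |
| Either ratio, class dose: SE 0.161; 0.206 | ×/÷ 1.32 | ×/÷ 1.43 |

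**Step 3: bias if exposure bends.** Take slope 1 up to 200 mg and 0.5 above. The expected fitted slope is 0.876 under both CV pairs.
- 400/200: line 2^0.876 = 1.84; truth 2^0.5 = 1.41.
- 500/400: line 1.25^0.876 = 1.22; truth 1.25^0.5 = 1.12.
- 500/15: line 33.3^0.876 = 21.6; truth (200/15) × 2.5^0.5 = 21.1.
- 500 mg mean: about 16% too high.

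With a slope of 1.5 above 200 mg, 400/200 is modelled as 2.18 against a true 2.83, and the 500 mg mean is about 14% too low.

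**Step 4: coverage of the 90% CIs.** From 4,000 simulated trials per scenario at CV 25/40%:

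| Truth | 400/200 and 500/400, line | Adjacent ratios up to 200 mg, line | Per-dose means, line |
|---|---|---|---|
| Log-linear | 0.89–0.91 | 0.89–0.91 | 0.89–0.91 |
| Slope 0.7 above 200 mg | 0.00 | 0.34 | 0.62–0.90 |
| Slope 0.5 above 200 mg | 0.00 | 0.05 | 0.29–0.91 |

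In the 0.5-slope case, 500/15 still covers 0.93 and 400/15 covers 0.91. Coverage of 400/200 and 500/400 is also 0.00 for both bends at CVs of 15/25% and 35/50%. Class-dose CIs cover about 0.89–0.92 in every scenario.

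**Step 5: power of a lack-of-fit comparison.** Line against class dose is a 4 df F test. At the 5% level its approximate power is 57–79% for the 0.5-slope bend and 22–33% for 0.7, over the two CV pairs in Step 2.

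**The case against.** The best defence is that the power model fits the stated aim. Proportionality asks whether the slope is 1; log-linearity is the model's assumption, not the question. The slope and its 90% CI are output, and they do respond to a bend. In the 0.5-slope case the expected interval is about 0.82–0.93 (0.876 ± 1.711 × 0.033), which excludes 1. A reader might infer that the plan cannot detect non-proportionality. It usually would here, though without showing where the curve bends. The geometric means by dose would also show a bend, but no CI for a dose contrast is listed with them.

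A reader might also infer that the CIs are simply too narrow. The documents do not support that as a general statement. Under log-linearity the CIs have their nominal coverage. Under a bend the failure is mainly bias, and the misfit even widens the slope SE a little (0.033 to 0.038 in the 0.5-slope case at CV 25/40%). Per-dose mean CIs are only 1.3–1.7 times narrower than class-dose CIs. Wide spans mostly hold, although 500/15 falls to 0.61–0.83 if exposure is flat only from 400 to 500 mg.

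It is also fair that 500/400, the smallest dose step, flatters the contrast in widths. A class-dose CI centred on 1.12 there would run from about 0.78–0.85 to 1.47–1.60, and so would not resolve the bend. The gain is an interval that does not depend on the line, not a sharper answer.

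These points limit the size of the problem. They leave the labelling and the missing check in place.

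**Conclusion.** The point holds as a matter of labelling and robustness. SAP 9.3.2 presents line predictions as treatment LS means and differences, and specifies no formal check of the line. If exposure bends, adjacent-dose ratios can be materially wrong with very tight intervals. In the 0.5-slope case 400/200 is overstated by about 30% (1.84/1.41), with almost no coverage.

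A tempting stronger reading is that these intervals feed exposure caps or dose choices in Parts B to D. The documents do not say so. Protocol 7.4.1 makes safety the primary criterion for escalation, with PK as support. Protocol 10.3.5 bases decisions on review of emerging data. SAP 10 plans no interim statistical analysis, and SAP 3 describes the plan as the template for the study report. The harm is therefore to the reported dose-proportionality results and to later planning.

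The sizes rest on assumed CVs and bend shapes, and on approximate degrees of freedom. They were worked out for Part A only; Part C shares the structure but was not quantified.

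**What to change.** - Keep the power model for the slope and its 90% CI in Parts A and C.
- Label any mean or ratio read from the line as model-predicted.
- Take per-dose LS means and dose-normalised ratios, with 90% CIs, from the same model with dose as a class effect (random subject in Part A, none in Part C).
- Compare the two models as a descriptive lack-of-fit check. State its limited power, so that a non-significant result is not read as proof of log-linearity.

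The cost is a few lines of SAS and wider CIs for adjacent-dose ratios. No new data are needed.

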9.4 Pharmacodynamic Assessment

9.4.1 Exploratory Pharmacodynamic Analysis

The DSST and HVLT will be included in Part C to assess relevant aspects of cognition, vigilance, and working memory that may provide a PD signal in healthy volunteers.

Endpoints from the DSST and HVLT will be summarized by domain (as appropriate), time, and treatment. Change from baseline (predose) will also be presented.

POMS-2: a profile of mood states is also included in Part C to assess subject transient, fluctuation feelings and enduring affect states. POMS-2 is a 35-item, adjective rating scale and is considered to be a standardized mood-state inventory. The change from baseline (predose) may be presented as applicable.

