Part A: Subjects will attend a screening visit up to 28 days prior to dosing in Period 1. Admission to the clinical research unit (CRU) will be in the afternoon of Day -2 of the first period and on Day -1 for Periods 2 and 3. After an overnight fast, subjects will receive either LY3154885 or placebo as a single oral dose on Day 1 and will remain inpatient for at least 48 hours after dosing (until Day 3), after which they may be discharged at the discretion of the investigator. The washout time between doses for a given subject will be at least 7 days. A poststudy follow-up visit will be conducted at least 7 days after the final dose.

Part B: Subjects will attend a screening visit up to 28 days before dosing. Subjects will be admitted to the CRU in the afternoon of Day -2 and will receive a single oral dose of LY3154885 or placebo on Day 1 after an overnight fast. There will be a 7-day washout period followed by 10 days of dosing with 200 mg itraconazole (twice daily on Day 8 [dose separated by 12 hours], then once daily on Days 9 through 17). Subjects will receive LY3154885 or placebo on Day 14, approximately 1 hour after the dose of itraconazole.

Part C: Subjects will receive either LY3154885 or placebo as a single oral once-daily dose from Days 1 through 14. Study drug will be administered as a single oral dose in the morning under fasted conditions. Subjects will attend a screening visit up to 28 days prior to dosing and will be admitted to the CRU in the afternoon of Day -2. After the initial dose (Day 1), subjects will be required to remain in-house for at least 48 hours after dosing (Day 3) and at the discretion of the investigator. Subjects will attend the CRU on Days 4, 5, 6, 9, and 10 on an outpatient basis for daily dosing and will be permitted to leave the CRU at the discretion of the investigator. A poststudy follow-up visit will be conducted approximately 7 days after discharge.

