12-lead ECG (hours)	X			Predose (-45 min, -30 min, -15 min)	Predose		Predose		Predose, (-45 min, -30 min, -15 min), 2, 3, 4, 6, 8, 12	24	X	X	Single safety ECGs at screening and ED/follow-up; triplicate ECGs at all other times. ECGs coinciding with PK sample time points are to be conducted as close as possible prior to PK sampling.	
PGx sample				X									Single sample for pharmacogenetic analysis taken prior to/on Day 1.	
Stored non-PGx plasma sample (hours)				Predose, 8			Predose		Predose, 8					
PK sampling (hours)				Predose, 0.5, 1, 2, 3, 4, 5, 6, 8, 12	Predose		Predose, 0.5, 1, 2, 3, 4, 5, 6, 8, 12	Predose (D8 only)	Predose, 0.5, 1, 2, 3, 4, 5, 6, 8, 12	24			Sampling times are relative to the time of LY3154885 administration (0 hour).	
POMS-2®			X			D6 only		D13 only						
Exploratory cognition assessments (HVLT, DSST)			X			D6 only		D13 only						
PWC-20				Predose						X	X	X		
C-SSRS and Lilly Self-Harm Supplement Form	X	X				D3 & D6 only		D8 & D10 only		X	X	X	Administer at screening, each admission, and each discharge from the CRU.	

Note: Site should schedule activities as appropriate. In cases where several study procedures are scheduled at the same time, follow this order of priority for procedures: ECG, vital signs, PK samples, clinical laboratory tests, biomarkers, and storage samples.

Abbreviations: ABPM = ambulatory blood pressure monitoring; AE = adverse event; BP = blood pressure; CRU = clinical research unit; C-SSRS = Columbia-Suicide Severity Rating Scale; D = day; DSST = Digital Symbol Substitution Test; ECG = electrocardiogram; ED = early discontinuation; HVLT = Hopkins Verbal Learning Test; MA = medical assessment; PE = physical examination; PGx = pharmacogenetic; PI = principal investigator; PK = pharmacokinetic; POMS-2 = Profile of Mood States Second Edition; PR = pulse rate; PWC-20 = Penn Physician Withdrawal Checklist.

Study Schedule Protocol J1Z-MC-HUAA (Part D: Formulations/Food Effect – 3 Study Periods)

		Periods 1, 2, and 3																
	Screening	Days														ED	Follow-up	Comments
Procedure	-28 to -3	-2	-1	1	2	3	4-6	7	8	9	10	11-13	14	15	16		Approx 7 days after discharge	
Informed consent	X																	
Admission to CRU		X	X				X D6					X D13						Admission on Day -2 is for Periods 1 and 2. Admission on Day -1 is for Period 3.
Discharge from CRU					X					X					X			
Medical history	X																	
AE/medication review	X		X	X	X	X	X	X	X	X					X	X		
Height/weight	X		X					X							X	X	Height at screening only	

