
Exploratory (Part C Only)
 
 • To explore any procognitive effects of LY3154885 in healthy subjects using the Hopkins Verbal Learning Test (HVLT) and Digital Symbol Substitution Test (DSST) • To explore the effect of LY3154885 on subjective mood using the Profile of Mood States Second Edition (POMS-2) • To evaluate any potential withdrawal symptoms following multiple once-daily dosing of LY3154885 	
HVLT and DSST
 
Effect on mood profile
 
Responses to Penn Physician Withdrawal Checklist (PWC-20)

5. Study Design

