10.3.3. Exploratory Pharmacodynamic Analyses

Endpoints from the DSST and HVLT will be summarized by domain (as appropriate), time, and treatment. Change from baseline may be displayed as appropriate.

Further details of analyses will be provided in the SAP.

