4.3 Exploratory Objectives (Part C Only)

- To explore any procognitive effects of LY3154885 in healthy subjects using the Hopkins Verbal Learning Test (HVLT) and Digital Symbol Substitution Test (DSST)
- To explore the effect of LY3154885 on subjective mood using the Profile of Mood States Second Edition (POMS-2)
- To evaluate any potential withdrawal symptoms following multiple once-daily dosing of LY3154885

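### Part C cognition and mood: the SAP shows placebo beside the doses but plans no LY3154885-minus-placebo estimate, and it does not name Day -1 as the baseline

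*SAP*

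**What the plan says.** The cognition objective in Protocol Section 4 and SAP 4.3 is "To explore any procognitive effects of LY3154885 in healthy subjects", using HVLT and DSST. A companion objective concerns the effect on mood, measured by POMS-2. Part C is randomised, blinded and placebo-controlled, with about 9 LY3154885 and 3 placebo subjects in each of three cohorts (SAP 5.3).

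The planned analysis is in SAP 9.4.1. For the cognition tests: "Endpoints from the DSST and HVLT will be summarized by domain (as appropriate), time, and treatment. Change from baseline (predose) will also be presented". For POMS-2: "The change from baseline (predose) may be presented as applicable". Protocol 10.3.3 is looser for DSST and HVLT ("Change from baseline may be displayed as appropriate") and leaves further detail to the SAP. SAP 9.1 restricts outputs: "Summary statistics and statistical analysis will only be presented for data where detailed in this SAP". SAP Section 6 lists one Placebo group for Part C ahead of the three dose groups.

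The Part C Schedule of Activities (Protocol Section 2) places HVLT, DSST and POMS-2 on Day -1, Day 6 and Day 13. Dosing runs from Day 1 to Day 14.

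**The concern.** Both objectives ask what the drug does, and in a randomised placebo-controlled part the quantity that answers this is the difference from placebo. The SAP stops one step short of it. It shows each arm's scores and changes and leaves the comparison to the reader, with no interval.

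This matters most for DSST and HVLT. One is a timed coding task and the other a word-list learning test (Protocol 9.6.1). Each is given on three days, and neither document mentions alternate forms, a training session or practice effects. A change within one dose arm is therefore the sum of any practice gain and any drug effect.

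The baseline label is a smaller gap. SAP 9.5.3 and 9.5.4 define baseline for laboratory data and vital signs as Day 1 predose. SAP 9.4.1 says only predose, and these tests have no Day 1 assessment. In the same schedule, PWC-20 does have a Day 1 predose entry. A programmer who carried the Day 1 convention over would find no record.

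The stake is how well a small data set is used. The protocol says the study's data will help design later studies, and side-by-side means from groups of about 9 do not show how uncertain a difference is.

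**Working it through.** **Plan's own figures.** No power, effect size, SD or correlation is given for these endpoints, so there is no precision figure to reproduce. The counts agree: 3 cohorts x 12 = 36 completers, of whom 3 x 9 = 27 are active and 3 x 3 = 9 are placebo. One dose against pooled placebo is therefore 9 v 9.

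**What is and is not planned.**
- DSST and HVLT: summaries by domain, time and treatment, plus change from baseline. No contrast, interval or model.
- POMS-2: optional change from baseline. No contrast, interval or model.
- QTcF in Part C (SAP 9.5.5.2): change from baseline with a placebo adjustment.
- PK comparisons (SAP 9.3.2): estimates with 90% CIs.

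The SAP thus already uses the Part C placebo arm in an estimate for one endpoint, and 90% intervals elsewhere.

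**Practice gain.** Let g be a practice gain common to all arms and d the drug effect. Expected change is g + d on a dose and g on placebo. The difference is (g + d) - g = d. Only the contrast isolates d.

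For scale, take the SD of a score as 1 and assume a test-retest correlation of 0.7 and g between 0.2 and 0.5 SD. These values are assumptions, not figures from the documents. The SE of the mean change in one 9-subject arm is sqrt(2(1 - 0.7)/9) = sqrt(0.6/9) = 0.258 SD. Practice alone then shifts that mean by 0.2/0.258 = 0.8 SE to 0.5/0.258 = 1.9 SE. The SAP plans no SE or test for this change, so the figures describe only the risk of reading one arm in isolation.

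**Precision of the contrast, 9 v 9, in SD units of the score.**
- Change score: SE = sqrt(2(1 - r) x 2/9).
- Adjusted for Day -1: SE = sqrt((1 - r^2) x 2/9).
- Variance ratio, adjusted to change: (1 - r^2) / (2(1 - r)) = (1 + r)/2.

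Half-widths use the error pooled over four arms, with 36 - 4 = 32 df for change and 36 - 4 - 1 = 31 df with the covariate.

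| Assumed r | SE, change | SE, adjusted | Variance cut | 90% half-width, change | 90% half-width, adjusted |
|---|---|---|---|---|---|
| 0.5 | sqrt(1.0 x 2/9) = 0.471 | sqrt(0.75 x 2/9) = 0.408 | 25% | 0.80 | 0.69 |
| 0.7 | sqrt(0.6 x 2/9) = 0.365 | sqrt(0.51 x 2/9) = 0.337 | 15% | 0.62 | 0.57 |

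The formulas ignore the small loss from chance baseline imbalance.

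**Pooling.** If only same-cohort placebo is used (9 v 3), the 90% half-width for change is about 1.21 SD of the change score, against about 0.82 with pooled placebo (two-sample t in both cases). Pooling buys that precision by assuming that cohorts run one after another do not differ systematically.

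**The case against.** The strongest reply is that these are exploratory endpoints in a study not powered for hypothesis testing, and that the descriptive plan matches the protocol. Placebo is shown in the same tables, so a common practice gain would be visible. SAP 9.1 gives mean, SD and N, from which a reader could work out a difference in change. SAP Section 3 also allows supplementary analyses. All of this is correct, and it keeps the point modest. It does not remove it. An analysis added later is chosen after the results are known, and a comparison that each reader must build is not a planned estimate.

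Several stronger readings are tempting, and the documents do not support them:

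- **That baseline is unscheduled or unused.** Day -1 precedes the first dose, so it is a predose score and the natural baseline. SAP 9.1 defines change as the value minus the subject's own baseline, so the planned change would use it. The defect is an unnamed visit.
- **That the SAP judges benefit by change within an arm.** It attaches no test, interval or decision rule to any arm's change.
- **That practice effects also distort POMS-2.** It asks how subjects feel at the moment, so a learning effect does not clearly apply. The case for a placebo contrast there rests on the objective alone.
- **That the size of the problem can be shown by pooling all active subjects, or by comparing adjusted with raw post-treatment scores.** The SAP lists the three doses separately and, for DSST and HVLT, commits to change scores. The fair comparator is therefore change in a single dose group.

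The schedule also gives no hour for the Day 6 and Day 13 tests. That belongs to the protocol schedule and is separate from this point.

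**Conclusion.** The point holds as a moderate improvement to an exploratory analysis. SAP 9.4.1 plans no LY3154885-minus-placebo estimate or interval for DSST, HVLT or POMS-2, although the design supplies a randomised placebo group and a pre-treatment score. A practice gain shared by the arms on DSST and HVLT would be visible but not removed from any estimate. Day -1 is the evident baseline but is not named.

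The gain from baseline adjustment over change scores is real but limited: 15% to 25% of variance for an assumed correlation of 0.7 down to 0.5. Even then the 90% half-width is about 0.57 to 0.69 SD, so only large effects could be told from none. These sizes rest on the assumed correlation, equal variances, 9 completers per group and pooling of placebo across cohorts. The absence of a planned contrast rests on none of them.

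**What to change.** In SAP 9.4.1:

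1. Name the Day -1 assessment as baseline for DSST, HVLT and POMS-2.
2. For each endpoint on Days 6 and 13, fit a model with treatment (each dose and pooled placebo) and the Day -1 score as covariate.
3. Report LY3154885 minus placebo for each dose with a 90% CI, labelled exploratory, and keep the by-treatment summaries beside it.
4. State that placebo is pooled across cohorts and that no multiplicity adjustment is made.

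This uses data already scheduled and needs no new subjects, visits or samples. The cost is SAP wording and one extra model per endpoint, giving 3 doses x 2 days = 6 intervals for each. The intervals will be wide. That is a drawback for presentation, but it states openly how little the data can settle.
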